## **12. Are there any hazards associated with the investigation?**

No known potential hazards will be introduced to participants.

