### **10.2 Method of selection of subjects**

The target population will be elderly living in Wuhan, Mainland China. The older adults participated in the previous cross-sectional study conducted by the principle investigator will be first invited.

Inclusion criteria for subjects to be screened are:

- 1) Chinese;
- 2) Aged 60 years and above;
- 3) No cognitive impairment or communication problems;
- 4) The angle of thoracic kyphosis  $> 40^\circ$  measured by Manual Inclinometer;
- 5) Able to decrease the angle of kyphosis of  $5^\circ$  while standing.

Exclusion criteria for subjects to be screened include:

- 1) Having central or peripheral neuropathy (this may affect balance);
- 2) Taking drugs that affect the nervous system or affect balance and strength;
- 3) Having untreated severe heart and lung disease (this may affect cardiopulmonary function);
- 4) Having a history of spinal fracture (this may increase the risk of injury);
- 5) Having surgery in spinal, shoulder, and pelvis in the past year or having plan to do so in the coming six month (this may increase the risk of injury);
- 6) Having scoliosis  $\geq 10^\circ$ ;
- 7) Having done any specific therapeutic exercise for posture in the past year or having plan to do so in the coming six month (may affect the study result).

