## **10. Methods of statistical analysis**

The data will be analyzed according to intention to treat. Descriptive statistics will be used to explore the characteristics of the elderly.

The primary outcome is the change in the angle of kyphosis. The secondary outcomes are the score change of pain and self-image, the change in score of the Farsi version of Functional Gait Assessment, change in time of the Timed Up and Go Test and the One Leg Standing Test, change in walking distance of the Six Minutes Walking Test, and change in length of the Chest Expansion test.

T-test and Chi-square test will be used to determine any baseline differences among two intervention groups and one control group in terms of baseline socio-demographics, regular exercise type and intensity, illness condition, and the angle of kyphosis.

Linear mixed effect model will be conducted to explore the between-group and within-group differences in the outcomes across the time, while controlling socio-demographics, illness condition, BMI, type and intensity of regular exercise. SPSS version 23.0 was used to analyze data collected, the significance level will be 0.05.

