## **11. Describe any unusual or discomforting procedures to be used**

Exposing the upper body in spine measurement may be embarrassing for some participants. In order to protect their privacy, the participant will be invited to a private room with air-conditioned, one at a time. The principal investigator and well-trained researcher helpers will perform the measurement. And the participants can stop measuring whenever they want to. For the measurement of physical fitness, participants may be tired. They can take a rest whenever they need.

In kyphosis-specific exercise class, the instructor participants ratio will be no less than 1:5 to endure the participants' safety. During exercise class, the participants can rest whenever they think is necessary. The first aid equipment will

be prepared. In the video exercise group orientation, the investigator will give exercise safety instruction.

Most of the exercises including in the kyphosis-specific exercise video are taking supine or prone posture, in order to prevent fall during exercise. In every follow up kyphosis-specific exercise classes, the certified physical trainer will reinforce safety instructions and exercise skills. The participants will be encouraged to contact the investigator whenever they have questions. No serious adverse event was reported by the previous studies letting older adults following exercise video doing home exercise.

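### No fall, injury or other adverse-event outcome is prespecified, elicited alike in both arms or compared by arm, although the protocol itself foresees injury and falls

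*Combined protocol and SAP*

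**What the plan says.** Section 12, on hazards, consists of one sentence: "No known potential hazards will be introduced to participants".

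Two other places treat injury and falls as foreseeable. Section 10.2 (selection of subjects) excludes people with a past spinal fracture, and people with recent or planned spinal, shoulder or pelvic surgery. The reason given each time is "this may increase the risk of injury". Section 11 (discomforting procedures) provides for a class staffing ratio, first-aid equipment and safety instruction, and says that most of the video exercises involve "taking supine or prone posture, in order to prevent fall during exercise". The safety evidence it offers is "No serious adverse event was reported by the previous studies letting older adults following exercise video doing home exercise".

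The section on methods of statistical analysis names change in kyphosis angle as primary. Its secondary list begins "The secondary outcomes are the score change of pain and self-image" and continues with gait, two balance tests, walking distance and chest expansion. No adverse event of any kind appears.

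Section 10.5 (procedures) gives both arms a log book. The intervention arm records home practice and other exercise and may write down questions, which the investigator answers weekly. The control arm receives a health-education booklet and records daily exercise time.

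**The concern.** Participants are aged 60 or over, and the intervention arm is asked to exercise at home from a video every day. The protocol's own background section says that the kyphosis-specific programmes it reviewed were all delivered face to face. The safety record it cites comes from home video exercise in general and covers serious events only. It therefore cites no safety record for this exercise in this form of delivery, and the trial is a natural place to collect one.

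If falls and injuries are not asked about during the trial, they cannot be reliably recovered at analysis. Any that do surface will come through channels that differ by arm. The report could then describe benefit by arm with no prespecified, comparable count of falls or injuries beside it.

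**Working it through.** The plan states no expected harm rate, harm threshold or safety sample size, so there is no safety figure to reproduce. The check is a comparison of the text, followed by arithmetic on how much 78 per arm could show.

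**Are injury and falls foreseen?** Yes. Section 10.2 gives injury risk as the ground for two exclusions, and section 11 gives fall prevention as the ground for the choice of postures. Section 11 says this of most exercises, not all, so the precaution is partial on its own terms.

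**Is an event outcome planned?** No. Every outcome in the statistical section is a change in a score, time, distance, length or angle. A participant who falls or strains a shoulder enters the analysis only through whatever effect remains on those measures at T1.

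**Would events be detected equally without a plan?** Not on the described contacts. The intervention arm has weekly trainer-led classes, a weekly investigator check of the log book and an invitation to write questions. The control arm is described only as having a booklet and an exercise-time log. Spontaneous reporting would favour detection in the intervention arm, so an ad hoc comparison could make exercise look worse than it is.

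**What could be learned if events were collected?**

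Inputs: 78 per arm and 20% drop-out (section 10.4), so 78 × (1 − 0.20) = 62.4, taken as 62 completers. Event rates of 1%, 2% and 5% are assumptions; the documents give none.

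Chance of at least one event in the intervention arm = 1 − (1 − p)^n:

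| Assumed rate p | n = 78 | n = 62 |
|---|---|---|
| 1% | 1 − 0.99^78 = 54% | 1 − 0.99^62 = 46% |
| 2% | 1 − 0.98^78 = 79% | 1 − 0.98^62 = 71% |
| 5% | 1 − 0.95^78 = 98% | 1 − 0.95^62 = 96% |

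One-sided 95% upper bound on the rate if no event is seen = 1 − 0.05^(1/n):

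- n = 78: 1 − 0.05^(1/78) = 3.8%
- n = 62: 1 − 0.05^(1/62) = 4.7%

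Power to compare two proportions, two-sided 5%, normal approximation: Φ{[|p1 − p0| − 1.96·√(2p̄(1 − p̄)/n)] / √[(p0(1 − p0) + p1(1 − p1))/n]}, with p̄ the mean of p0 and p1:

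- Assumed 5% against 15%: 55% with 78 per arm, 46% with 62.
- Assumed 5% against 20%: 81% with 78 per arm, 72% with 62.

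A table of counts with intervals would therefore be useful for common events. A formal test between arms would have reasonable power only for a large difference.

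**The case against.** Several arguments on the other side are sound and limit the point.

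- **The hazard statement is not shown to be false.** A reader might infer that section 12 is flatly contradicted elsewhere. But excluding people at raised risk and choosing safer postures are mitigation, and the sentence can be read as meaning that no known hazard remains after those measures. The passages are in tension and need reconciling; they are not logically incompatible for those enrolled.
- **Nothing shows that ethics review was misled.** The documents do not say what that review relied on, section 11 stands directly before section 12, and the information sheet and consent form are not available to judge.
- **Some comparative information on harm is planned.** A mean worsening of pain, gait, balance or walking distance would appear in the mixed model. It would be wrong to say that the trial has no comparative harm data at all. These means do not count falls or injuries, however, and pain enters as a hypothesised benefit.
- **The appendices may capture events.** Appendix 1 (questionnaires) and Appendices 6 and 7 (log-book pages) are not shown. Some recording there cannot be ruled out, so the firm claim is limited to the described procedures and to the absence of any planned analysis.
- **Safety is not a stated aim, and safeguards exist.** Weekly classes, log-book checks, safety instruction and encouragement to contact the investigator all lower the stakes. None of them is systematic recording in both arms.

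**Conclusion.** The point stands in a limited form. In the text available, falls, injuries and other adverse events are not prespecified as outcomes, not elicited in the same way in both arms and not compared by arm, although the protocol itself anticipates injury and falls. As planned, the trial has no prespecified comparative basis for a statement about such events.

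With collection in place, an event with a true rate of 5% would very probably be seen at least once (96% to 98%), but one with a rate of 1% would be missed about half the time. Zero events would exclude only rates above 3.8% to 4.7%. These figures rest on the assumed rates and on between 62 and 78 participants being observed.

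A reader might infer that adding an event outcome would let the trial show that the exercise is safe. It would not: the trial could describe common events and could not establish safety for rare ones. This is a worthwhile, inexpensive improvement. It does not undermine the primary analysis.

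**What to change.** - Add an entry for falls, injuries and other adverse events to the log books that both arms already receive, with identical wording.
- Ask both arms the same question at T1. Because assessors are to be blinded, place it after the angle and performance measurements, so that an answer which reveals allocation cannot affect them.
- In the section on methods of statistical analysis, add a descriptive safety outcome: number of events and number of participants affected, by arm, with confidence intervals. State that no formal test is intended and that rare events are beyond the trial's reach.
- If Appendix 1, 6 or 7 already records such events, refer to it there and confirm that the wording is the same in both arms.
- Reconcile section 12 with the injury and fall risks acknowledged in sections 10.2 and 11.

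The cost is a slight burden on participants and one extra table. Participants are not blinded, so some difference in reporting may remain even with identical questions; the report should say so. No change to the exercise programme or to clinical management is involved.

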## **13. Direct access to source data/documents**

The principal investigator is responsible for processing and storing the raw data during and after the completion of the study. Three copies of the raw data will be stored as encrypted files on the principal investigator's computer, external hard drive, and reliable networked cloud.

## **14. Consent**

In order to respect the principles of human dignity, when approaching the participants, the researcher will explain the purpose and steps of the study based on the information sheet (Appendix 3). The researcher will also emphasize that joining the study will be entirely voluntary and every participant has the right to withdraw or refuse to give information at any time during the study without incurring any penalties. Eligible participants will sign a consent form (Appendix 5).

